**Randomization.** Within 72 hours of life and within 24 hour of initiating feeds of less than 20 mL/kg/d, informed consent will be obtained from the mothers, and infants will be randomly assigned to one of two groups by random length permuted blocks of sizes 4, 6, or 8 to maintain approximate balance assigned to each treatment group.

**Standard Infant Feeding Protocol.** As per standard NICU protocol, all infants will begin receiving PN within 24 hours of life. In addition, all infants will have an orogastric (OG) or nasogastric (NG) tube placed upon admission to the NICU and begin receiving enteral feeding of less than 20 ml/kg/d within 72 hours. Length of insertion of the OG/NG tube is determined by measuring from the tip of the nose to the tip of the ear lobe and then halfway between the xiphoid process and umbilicus (Ellett et al., 2011). Minimum insertion length based on the weight of the infant (Cordero et al., 2011). If the infant receives an X-ray upon admission, placement of the OG/NG tube is verified. Placement is also verified if additional X-rays are taken during the study as per usual OG/NG placement protocol in the NICU. Depending on the infant's gestational age, weight, and clinical status, feedings are initiated at up to 20mL/kg/d and advanced daily by no more than 20mL/kg/d toward a goal of 120-150mL/kg/d divided into 8 equal feedings per day using the established University of Florida Children's Hospital NICU feeding guidelines. Mom's own breast milk is encouraged, and donor breast milk provided if mothers own breast milk is unavailable. Prior to each feeding, the OG/NG tube is checked for proper placement by the bedside nurse verifying the insertion length with the initial measured insertion length. In addition, the nurse assesses the infant for any signs or symptoms of feeding intolerance or NEC (i.e., abdominal distension and/or tenderness, increased abdominal girth, visible bowel loops, presence of emesis, and visible blood in the stool). It is standard protocol to aspirate RGC prior to each feeding. However, for this study, this will only occur in infants randomized to Group 1. Kangaroo Care (holding of an infant dressed only in a diaper upon someone's bare chest) can positively affect growth and improve feeding tolerance (Conde-Aquedelo et al., 2011) Kangaroo care is encouraged in this NICU and nursing protocols have been established to provide support to all mothers regarding provision of kangaroo care.

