**Research Procedure.** The procedures used in this study will be the same as those successfully used in the preliminary study. Following consent by the mothers, infants will be randomized, and baseline demographic data will be collected from their medical charts. Over the first 6 weeks of life the following additional information will be collected at specified time periods from their medical charts: weekly enteral intake, days to full enteral feedings (120 mL/kg/d), hours of PN, evidence of PNALD (level of direct bilirubin, alkaline phosphatase, aspartate aminotransferase (AST) and alanine aminotransferase (ALT)), growth indices (weekly weight, head circumference and length), medications, hours with a CVL, episodes of presumed or culture proven LOS (occurring > 7 days of life), days to discharge, evidence of stage 2 or greater NEC, evidence of aspiration pneumonia on chest radiograph, episodes of ventilator associated pneumonia and guaic status of stools. Additionally, one stool sample will be collected at 3 and 6 weeks to test for fecal calprotectin levels. 1mL of blood will be collected during a routine blood draw between 7 and 14 days of life to test for serum gastrin and motilin levels. If ventilated, tracheal aspirate samples will be collected on days 1, 3, 5, 7, 14, 21, 28 and 35 from routine tracheal aspirate suctioning. As kangaroo care is a potentially confounding factor, episodes and duration of kangaroo care between mother and infant will be recorded on the Kangaroo Care log sheet located at the infant's bedside by either the mother or the nurse. See Table 1.

**Aim 1.** The primary aim of this study is to determine the risks and benefits of aspirating RGC and the clinical benefits of omitting aspiration of RGC prior to enteral feedings on the nutritional outcomes of premature VLBW infants. Both groups will have a sign placed on their isolettes stating which group they are assigned to and whether the nurse should or should not aspirate RGC. Although already documented on the infant's flow sheet, the sign will also include an area for the nurse to document the OG/NG insertion depth. Those personnel who are not involved with the study infants will be unable to be blinded since information regarding gastric residual volume and color is placed in the chart by the nursing staff and monitored by clinicians making decisions regarding enteral feeding plans. The PI is a neonatal nurse practitioner in the NICU

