**Aim 3.** Aim 3 will determine the effect of routine RGC aspiration on gastrointestinal function as evidenced by gastrointestinal peptide activity. Serum levels of gastrin and motilin will be measured on all infants between 14 and 21 days depending upon the timing of a routine blood draw. Since all GRCs are not discarded, waiting until between 14-21 days will allow adequate time for potentially one or more GRC to be discarded. 1 mL of blood will be taken during a routine blood test. All samples will be sent to the laboratory at Shands Children's Hospital at the University of Florida for testing, and lab values will be extracted and recorded by the project coordinator.

**Statistical Analysis.** Data will be entered into the RedCap system by the research assistant. For the primary hypothesis (P1.1), the total weekly enteral intake will be compared between the two randomized treatment groups via a two-sided Welch-corrected T-test. For sample sizes of this magnitude, the central limit theorem assures us that this is an assumption-free analysis, even if the underlying population variances differ. An interim analysis of P1.1 will also be done as described in the Power Analysis section below. Secondary hypotheses S1.1-S1.7 will be tested in the same manner as the primary hypothesis P1.1. For secondary Hypothesis S2.1 (S3.1), [S3.2], we shall compare the personal fractions of positive stools (gastrin levels) [motilin levels] respectively via two-sided Welch-corrected T-tests. For secondary hypothesis S2.2, we shall use a repeated measures analysis of variance to compare the groups with respect to week 3 and week 6 calprotectin levels. . Actual P-values will be reported, and each hypothesis will be accompanied by a point estimate and 95% confidence interval estimate for effect size. For descriptive purposes, a P-value of under 5% will be declared significant. The study is powered strictly around the primary hypothesis P1.1. Withdrawal rates will be compared between the treatments in a tertiary manner using survival analysis (time to withdrawal), via a logrank test.

**Expected outcomes.** Based on the preliminary study, it is reasonable to expect that infants who do not receive routine aspiration of RGC will have better nutritional outcomes, evidence of less gastrointestinal bleeding and inflammation, and improved gastrointestinal function.

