**Table 1. Instruments**

Variable	Measurement
Demographic data	Gestational age, birth weight, maternal history, prenatal and perinatal complications and medication, mode of delivery, Apgar scores, resuscitation at birth and neonatal acuity (SNAP II) score, medications and disease processes associated with decreased intestinal motility, episodes and duration of KC
Nutritional factors (1-8) below	
1. Enteral intake	Weekly 24-hour enteral feeding intake in mL/kg for first 6 weeks; Type of feeding received
2. Time to full feeds	First day infant received $\geq 120$ mL/kg/d of enteral feedings
3. Hours of TPN	Number of hours infant received some PN for days 1-42
4. PNALD	Weekly or biweekly liver function tests (level of direct bilirubin, alkaline phosphatase AST and ALT) for first 6 weeks
5. Hours of central venous line access	Number of hours infant has a central venous line for days 1-42
6. Episodes of late onset sepsis	Episodes of culture proven or presumed sepsis (treated with 7-10 days of antibiotics but with negative cultures) during week 1- 6 weeks of life
7. Growth indices	Weekly weight, length, and head circumference
8. Length of hospital stay	Days infant remains in hospital from birth until discharge
Episodes of NEC	Episodes of radiologic evidence of NEC during the first 6 weeks
Gastrointestinal bleeding and inflammation (1-2) below	
1. Presence of blood in stools	Positive or negative guiac of all stools for first 6 weeks
2. Fecal calprotectin levels	Level of fecal calprotectin at 3 and 6 weeks
Gastrointestinal function	Serum levels of gastrin and motilin at 14-21 days
Respiratory aspiration of gastric contents (1-3) below	
1. Pepsin level in tracheal aspirates	Pepsin level in the tracheal aspirates of ventilated infants on day ,7,14, 21, 28 and 35
2. Presence of aspiration pneumonia	Presence of aspiration pneumonia on all radiographs
3. Presence of ventilator associated pneumonia	Presence of positive tracheal aspirate on ventilated infants

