**Table 2: Timetable for Collection of Data**

Data	Time Period Collected
Demographic data	Upon entry into study and during 6 week study period
24-hour enteral feeding intake in mL/kg	Weekly for 6 weeks
Time to full feedings	Recorded daily until 120mL/kg/d reached
Hours of PN	Daily for 42 days
Evidence of PNALD	Weekly or biweekly liver function tests (level of direct bilirubin, alkaline phosphatase AST and ALT )for first 6 weeks
Hours of central venous line access	Daily for 42 days
Episodes of late onset sepsis	All incidences of culture proven or presumed (treated for 7-10 days but with negative cultures) for weeks 1-6.
Growth indices	Weekly weights, head circumferences and lengths
Days to discharge	Days infant is hospitalized
Episodes of radiologic evidence of NEC	All incidences for 6 weeks
Results of stool guaiac	Every stool for 6 weeks
Fecal calprotectin levels	3 and 6 weeks
Serum levels of gastrin and motilin	14-21 days
Pepsin level of respiratory aspirate	Day 1,3,5,7,14 21, 28 and 35 in ventilated infants
Evidence of aspiration pneumonia	All radiographs for 6 weeks
Respiratory cultures	All respiratory cultures done on ventilated infants for 6 weeks

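### The single gastrin/motilin blood draw is set at 7-14 days in Research Procedure but at 14-21 days in Aim 3, Table 1 and Table 2; the windows share only day 14

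*Combined protocol and SAP*

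**What the plan says.** Four places in the combined protocol and SAP give a time for the gastrin and motilin sample.

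- **Research Procedure:** 1 mL of "blood will be collected during a routine blood draw between 7 and 14 days of life to test for serum gastrin and motilin levels". The paragraph ends by sending the reader to Table 1.
- **Aim 3:** "Serum levels of gastrin and motilin will be measured on all infants between 14 and 21 days", again as 1 mL from a routine blood test. The reason given is that "waiting until between 14-21 days will allow adequate time for potentially one or more GRC to be discarded".
- **Table 1 (Instruments):** "Serum levels of gastrin and motilin at 14-21 days".
- **Table 2 (Timetable for Collection of Data):** "Serum levels of gastrin and motilin 14-21 days".

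The values feed secondary hypotheses S3.1 (gastrin) and S3.2 (motilin). For these the Statistical Analysis section says "we shall compare the personal fractions of positive stools (gastrin levels) [motilin levels] respectively via two-sided Welch-corrected T-tests". That is one value per infant, with no term for age at sampling. The same section states that power was set for P1.1 only.

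**The concern.** The sampling instruction in the procedural section contradicts the aim it serves and both tables. A coordinator has good reason to work from Research Procedure, which also says that its procedures are those of the preliminary study. A coordinator working from Table 2 would sample a week later. As written, a sample on day 9 is on schedule under one section and out of window under three.

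The timing has a purpose. Aim 3 links it to exposure: enough time must pass for residuals to have been discarded. Gastrin and motilin are the only measurements listed for that aim, and no repeat draw is described, so a mistimed sample cannot be recovered. If one window is used throughout, a later reader cannot tell from the protocol which one it was. If both are used, infants of different ages and cumulative exposure are pooled in an unadjusted comparison.

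**Working it through.** **Could both statements be true?** Only if two samples were planned. Research Procedure and Aim 3 each describe 1 mL from a routine draw for the same two peptides. Table 2 lists one window, and no section mentions serial sampling. Two draws is not a plausible reading.

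**Overlap of the windows, in whole days with both ends included**

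- Research Procedure: days 7 to 14, which is 14 − 7 + 1 = 8 days.
- Aim 3 and both tables: days 14 to 21, which is 21 − 14 + 1 = 8 days.
- Shared: day 14 only, so 1 of 8 days in each window (12.5%) and 1 of the 15 days the two span together.
- Days 7-13 satisfy only Research Procedure. Days 15-21 satisfy only the other three places.

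**Scheduled exposure at the draw.** Standard Infant Feeding Protocol gives feeds "divided into 8 equal feedings per day" and has infants "begin receiving enteral feeding of less than 20 ml/kg/d within 72 hours". In Group 1, residuals are aspirated before each feed. Assuming 8 feeds a day from the first day of feeding and none held:

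scheduled aspirations by a given day = (day − day feeds start) × 8

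| Feeds start | Day 7 | Day 14 | Day 21 | Midpoint of 7-14 (day 10.5) | Midpoint of 14-21 (day 17.5) | Ratio of midpoints |
|---|---|---|---|---|---|---|
| 72 h (day 3) | 4 × 8 = 32 | 11 × 8 = 88 | 18 × 8 = 144 | 7.5 × 8 = 60 | 14.5 × 8 = 116 | 60/116 = 0.52 |
| 24 h (day 1), assumed | 6 × 8 = 48 | 13 × 8 = 104 | 20 × 8 = 160 | 9.5 × 8 = 76 | 16.5 × 8 = 132 | 76/132 = 0.58 |

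The 72 h start is the latest the protocol allows for first enteral feeds. The 24 h start is an assumption used to show a range; the documents attach 24 h to parenteral nutrition.

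Two things follow. A sample in the earlier window is not a pre-intervention sample, because dozens of aspirations are already scheduled by day 7. At the midpoints, it follows a little over half as many as a later sample.

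**What cannot be computed.** The documents give no expected difference, no standard deviation and no discard rate for this aim, so a loss of power or precision cannot be put into numbers.

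**The case against.** The case for treating this as minor has weight. Three of the four statements agree. They include the timetable for data collection and the only text that gives a reason, and the outlying paragraph itself refers to Table 1. Staff may well have used 14-21 days throughout. That makes the worst case less likely, but the protocol states no order of precedence, and the outlier sits in the section that tells staff what to do.

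A second objection is that the exposure count measures the wrong thing. Aim 3's reason concerns residuals that are discarded, not residuals that are aspirated. This stands. Without a discard rate, 52% or 58% of scheduled aspirations says nothing firm about the share of discards. The counts are also totals rather than a contrast between arms: randomization may follow the first feed by up to 24 hours, and aspiration is standard care until then. Removing 8 aspirations from the 24 h scenario gives 68 against 124, or 55%, which changes little.

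A third objection is that dilution requires the effect to grow with cumulative exposure, and added variability requires the peptides to change with age. The documents establish neither, so both are possible consequences and not demonstrated ones. Likewise, how many samples would fall before day 14 depends on when routine blood draws happen, which is not stated.

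None of this removes the contradiction.

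**Conclusion.** The concern holds. The protocol gives two windows for one sample, overlapping on a single day, and nothing reconciles them. Followed as written, Research Procedure puts 7 of its 8 permitted days before the interval that Aim 3 calls adequate.

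The scale is modest. What is at stake is possible dilution and extra variability in S3.1 and S3.2, both unpowered secondary endpoints. Bias between arms is not the expected result, since the ambiguity is the same for both groups. P1.1 and the sample size do not depend on it. The overlap result rests on the text alone. The exposure ratios of 52% to 58% rest on 8 feeds a day, no held feeds and a feed start between 24 h and 72 h, and they describe aspirations rather than discards. The correction should be made, but it does not threaten the trial's main conclusion.

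**What to change.** Reconcile Research Procedure, Aim 3, Table 1 and Table 2 so that one sampling window appears in all four. This review does not say which window is right. It notes only that the written rationale covers 14-21 days, so choosing the other window would call for a rationale of its own.

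Record the postnatal day of each gastrin/motilin draw, so that timing can be reported by group and out-of-window samples identified. An analysis adjusted for draw day is optional and should be supporting only; the planned Welch tests can stay.

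The cost is a one-line protocol correction and one date per infant. The sample already comes from a routine draw, so no extra blood or procedure is needed.

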**Aspiration of Gastric Residual Contents**

**NCT 01863043**

**3/4/2016**

## Protocol

**Research Design.** A randomized clinical trial will be conducted to determine the benefits of omitting aspiration of residual gastric contents (RGC) prior to feedings on nutritional outcomes and gastrointestinal integrity and functioning of premature, very low birth weight (VLBW) infants. VLBW infants will be randomly assigned to one of two groups. Group 1 will receive standard care; that is, physical parameters of feeding intolerance and NEC will be assessed and RGC will be aspirated prior to each feeding. In Group 2, physical parameters for feeding intolerance and NEC will be assessed but RGC will not be aspirated. To determine nutritional outcomes, the following factors will be evaluated: (1) weekly enteral intake for the first 6 weeks of life, (2) time to reach full enteral feedings, (3) hours of parenteral nutrition (PN), (4) diagnosis of parenteral nutrition associated liver disease (PNALD), (5) growth indices, (6) hours of central venous line (CVL) access, (7) episodes of late onset sepsis (LOS), (8) length of hospital stay. The presence of gastrointestinal bleeding and inflammation will be measured by (1) presence of blood in the stool, and (2) fecal calprotectin levels. Furthermore, plasma levels of gastrointestinal peptides including serum gastrin and motilin will be measured as indicators of gastrointestinal function. See Table 1.

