**Sample and Setting.** The proposed study will follow a prospective cohort ( $N = 120$ ) of racially and economically diverse VLBW infants for 6 weeks following birth. The infants will be born to mothers who are English or Spanish speaking and who are 18 years of age or older. VLBW infants will be sampled by convenience from the neonatal intensive care unit (NICU) at Shands Children's Hospital, a Level III tertiary care center. The hospital is part of the University of Florida and includes a 52 bed NICU. The hospital catchment area encompasses north central Florida and southern Georgia, a predominantly rural and semi-rural population. Approximately 100-110 VLBW infants are delivered there per year. In the preliminary study, 70% of mothers consented for the study. Inclusion criteria for the infants are as follows: (1) born at 32 weeks or less of gestational age, (2) birth weight equal to or less than 1,250 grams, and (3) infant receiving some enteral feedings by 72 hours of age and parenteral feedings by 24 hours of age. Exclusion criteria for the infants are as follows: (1) congenital or chromosomal abnormalities, (2) complex congenital heart diseases and congenital anatomic gastrointestinal abnormalities, (3) Infants will be withdrawn from the study if any of the following occur: grossly bloody stools, radiologic evidence of NEC, or other intestinal complications such as perforation.

**Sample Size Determination / Power Analysis.** In the preliminary study, 40 premature, VLBW infants had a mean enteral intake at 14 days of 72 mL/kg/d ( $SD=65$ ). To detect a 50% improvement to 108, we would require 104 evaluable subjects in a non-sequential design for Primary 1.1 to achieve 80% power at  $P=0.05$  (two-sided). To accommodate one interim analysis, we employed the minimax method of Shuster et al (2002), with first look after 66 evaluable subjects have been accrued. If  $|Z|>2.28$  we shall stop for significance. If  $|Z|<1.12$ , the study will be reviewed for possible futility. There will be no stopping for futility. Otherwise, the study will accrue 120 evaluable subjects (54 more). No competing two stage design can achieve a lower worst case scenario average sample size than this one's 89 evaluable. Intent-to-treat will be followed as closely as possible. However, to accommodate dropouts including deaths (15%) and infants who develop NEC (7%) we expect to accrue 160 subjects.

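### The sample size for P1.1 rests on enteral intake at 14 days, but the test is written for a total weekly intake that is never reduced to one value per infant

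*Combined protocol and SAP*

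**What the plan says.** Four places in the combined protocol and SAP bear on P1.1.

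- **Sample Size Determination / Power Analysis.** The 40 pilot infants "had a mean enteral intake at 14 days of 72 mL/kg/d" with SD 65. For an improvement to 108, "we would require 104 evaluable subjects in a non-sequential design for Primary 1.1 to achieve 80% power", two-sided at 0.05. One interim look follows at 66 evaluable infants, with a stop for significance at |Z| > 2.28; otherwise accrual continues to 120.
- **Statistical Analysis.** For P1.1, "the total weekly enteral intake will be compared between the two randomized treatment groups via a two-sided Welch-corrected T-test". The section adds "An interim analysis of P1.1 will also be done as described in the Power Analysis section below" and "The study is powered strictly around the primary hypothesis P1.1".
- **Research Design.** The first nutritional factor is "weekly enteral intake for the first 6 weeks of life", with no day singled out. Research Procedure also lists weekly intake over six weeks.
- **Tables 1 and 2.** The measurement is "Weekly 24-hour enteral feeding intake in mL/kg for first 6 weeks", collected weekly. Neither table says on which day of the week the value is taken.

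**The concern.** A two-sample t-test needs one number per infant. The test sentence calls that number a weekly total, the tables supply six separate 24-hour values, and the sample size was computed for a daily rate at 14 days. The tables do define the raw measurement and its unit. What is missing is the step from six values to the one that is tested.

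Two things follow. First, the only documented power belongs to a variable that the test sentence does not name, although the plan says that its power rests strictly on P1.1. Second, the choice of week or summary is still open when the interim efficacy look arrives, in a trial whose feeding decisions are made by unblinded clinicians. The primary variable should be settled before anyone sees a comparison.

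**Working it through.** **Inputs from the Power Analysis section:** means 72 and 108, so a difference of 36 mL/kg/d; SD 65, taken as common to both arms; two-sided 0.05; 80% power; looks at 66 and 120 evaluable. Allocation is approximately 1:1 (Randomization section).

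**1. Reproduce the plan's figure on the day-14 variable.**
- Standardized difference: 36/65 = 0.554.
- n per arm = 2 × (1.960 + 0.842)² / 0.554² = 51.2, rounded up to 52, so 104 in total. This matches the plan.
- Power at 104: 80.6% (normal approximation) or 79.9% (noncentral t).

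**2. Two-look design on the same variable.** The documents give no final critical value, so I derived one. The correlation between looks is √(66/120) = 0.742. With 2.28 at the first look and no futility stop, an overall 5% needs a final bound of 2.088. Power at 0.554 SD is then 83.9% (normal approximation).

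**3. What another variable would need.** Power depends only on the ratio of difference to SD. For 80% power that ratio must be at least
- 0.555 at 104, fixed design (noncentral t);
- 0.527 at 120 with the two looks and the derived bound.

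The documents give no difference or SD for any weekly or six-week summary, so this cannot be checked for them.

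**4. Illustration of the spread (assumptions, not document figures).**
- Seven-day total equal to exactly 7 times the daily value: difference 7 × 36 = 252, SD 7 × 65 = 455. The ratio is unchanged, so 104 is needed again.
- Mean of the six weekly values, assuming SD 65 each week and between-week correlation r: SD of the mean = 65 × √((1 + 5r)/6), which is 42.0 at r = 0.3 and 56.3 at r = 0.7.

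| Assumed weekly differences | Mean difference | Total N for 80% (r = 0.3 to 0.7) | Fixed-design power at 120 |
|---|---|---|---|
| 36 in every week | 36.0 | 44 to 78 | 99.7% to 93.9% |
| 10, 36, 36, 20, 10, 0 | 112/6 = 18.7 | 160 to 286 | 68.3% to 44.3% |

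The sum of the six values has the same ratio as their mean, so the table covers both. The direction depends wholly on the assumed pattern.

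**5. Covariate adjustment (separate from the mismatch).** If baseline covariates explain a share R² of the variance, the residual SD is 65 × √(1 − R²). Fixed-design power at 104 by the noncentral t rises from 79.9% to 83.9% (R² = 0.1), 87.9% (0.2), 91.7% (0.3) or 95.1% (0.4). These R² values are assumed; the documents give none.

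**The case against.** The strongest reply is that the plan can be read as coherent. The Statistical Analysis section ties power to P1.1 and sends the interim analysis to the Power Analysis section, where the only outcome variable is intake at 14 days. A reader might infer that day 14 was therefore the likeliest intended endpoint and that the test sentence is loose wording. The documents do not support going that far. Reproducing 104 shows which variable was used for sizing, not which was meant for testing. The test sentence speaks of a weekly total, and Research Design, Research Procedure and both tables describe weekly intake over six weeks. For the intake outcome, 14 days appears only in the sizing paragraph. The full wording of hypothesis P1.1 is not in the public text, so intent cannot be settled from it.

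A reader might also argue from the feeding plan, in which feeds are "advanced daily by no more than 20mL/kg/d toward a goal of 120-150mL/kg/d", that differences and SDs must both shrink in later weeks. That does not follow. The range is a goal, feeding advancement also depends on signs of intolerance, infants below goal stay in the comparison, and no section reports intake after day 14.

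A further fair point is that no demonstrated harm follows from the ambiguity. That stands: the defect is in what is specified, not in a computed loss.

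**Conclusion.** The mismatch is real and concerns the primary endpoint. The power section, the test sentence and the data tables describe three different quantities, and nothing says which one enters the Welch test at either look. The stated 104 is correct for the day-14 value, at about 80% power; this assumes a common SD of 65 and equal arms. The 83.9% for the two-look design rests in addition on my derived final bound.

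For any weekly or six-week summary, power is undocumented and could be higher or lower. A reader might infer that the trial is underpowered, but the lower figures above come only from assumed patterns, and other assumed patterns give more than 90%. Nor is an inflated type I error shown: the plan describes a single comparison, and the |Z| > 2.28 bound, paired with a matching final bound, controls error for any one variable fixed in advance. The gap is that the variable has not been fixed. This should be corrected, and it does not put the sample size in doubt if the day-14 value is chosen.

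**What to change.** Before the interim look, state in the Statistical Analysis section the one variable that P1.1 tests: the day or week, the unit, the summary, and how infants who die or are withdrawn before it is measured are handled. The last item matters because the plan itself expects 15% dropouts including deaths and 7% NEC. Use the same variable at the interim and final analyses, and align the Power Analysis section and Tables 1 and 2 with it.

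- **24-hour intake on day 14 (mL/kg/d).** This option keeps the stated sample size and power. It costs a sentence in the analysis section, a line in each table fixing the week-2 value to day 14 (to be confirmed against how data are collected), and a rule for infants lost before then. The other weeks become secondary.
- **A weekly or six-week summary.** Define it (sum or mean, which days, missing weeks), justify its own difference and SD, and restate the power. The sample size may change.

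A separate and optional improvement, since the unadjusted Welch test is valid: prespecify adjustment of the P1.1 comparison for birth weight and gestational age, with robust standard errors, at both looks. Both are already collected, so the cost is analysis text only. At an assumed R² of 0.1 to 0.4, fixed-design power at 104 would rise from 80% to about 84% to 95%.

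### The primary test ignores gestational age, birth weight and acuity, which the plan says drive feeding and already records, so precision is given up at no saving.

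*Combined protocol and SAP*

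**What the plan says.** All references are to the combined protocol and SAP.

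- **Statistical Analysis.** The outcome for P1.1 is described as "compared between the two randomized treatment groups via a two-sided Welch-corrected T-test. For sample sizes of this magnitude, the central limit theorem assures us"; the sentence goes on to claim freedom from distributional assumptions, even with unequal variances. S1.1 to S1.7 are tested in the same way. No adjusted analysis is planned, either as primary or as sensitivity analysis.
- **Randomization.** Infants are allocated by "random length permuted blocks of sizes 4, 6, or 8 to maintain approximate balance assigned to each treatment group". No stratification factor is named. Blocking balances the number of infants per arm, not their maturity.
- **Standard Infant Feeding Protocol.** "Depending on the infant's gestational age, weight, and clinical status, feedings are initiated at up to 20mL/kg/d", and daily advancement is governed by the same sentence.
- **Table 1.** The first row collects "Gestational age, birth weight, maternal history, prenatal and perinatal complications and medication", and further along the SNAP II score. Gestational age and birth weight are also inclusion criteria under Sample and Setting.
- **Sample Size Determination / Power Analysis.** From a preliminary mean of 72 mL/kg/d with SD 65, and a target of 108, the plan states that "we would require 104 evaluable subjects in a non-sequential design for Primary 1.1". It then sets one interim look at 66 evaluable infants, stopping for significance if |Z| exceeds 2.28, and a maximum of 120.

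**The concern.** The primary outcome is enteral intake, and the plan itself says that gestational age, weight and clinical status help determine how feeds start and advance. This prognostic claim comes from the protocol, not from outside literature. An SD of 65 on a mean of 72 is large, and some of it is plausibly variation that these variables would explain.

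Two things are at stake. An unadjusted test leaves that variation in the standard error, so the confidence interval is wider and power lower than the same infants could give. It also leaves any chance imbalance in maturity inside the treatment estimate. That matters most at the interim look, where about 33 infants per arm could stop the trial.

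The justification offered, the central limit theorem and tolerance of unequal variances, concerns validity. It does not address precision.

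**Working it through.** **Inputs from the plan.** Difference 108 − 72 = 36 mL/kg/d; SD 65; two-sided 0.05; 80% power; looks at 66 and 120 evaluable; interim boundary 2.28. **Assumed input.** R², the share of outcome variance explained by the baseline covariates. The documents give none, so 0.1 to 0.4 is shown.

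**1. The plan's own figure.** n per arm = 2 × (1.960 + 0.842)² × 65² / 36² = 2 × 7.849 × 4225 / 1296 = 51.2, rounded up to 52. The total is 104, which matches the plan exactly. The trial was therefore sized on the full, unadjusted SD.

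**2. Effect of adjustment.** Residual SD = 65 × √(1 − R²). The standard error shrinks by 1 − √(1 − R²), and the required N scales with (1 − R²). Power and detectable difference below use the two-sample t distribution (noncentral t) with 60 per arm and a single look.

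| Assumed R² | Residual SD | Fall in SE | N for 80% power (formula of step 1) | Power for 36, 60 per arm | Difference detectable at 80% power (mL/kg/d) |
|---|---|---|---|---|---|
| 0 (as planned) | 65.0 | – | 104 | 85.3% | 33.5 |
| 0.1 | 61.7 | 5% | 94 | 88.7% | 31.8 |
| 0.2 | 58.1 | 11% | 82 | 92.0% | 30.0 |
| 0.3 | 54.4 | 16% | 72 | 94.9% | 28.0 |
| 0.4 | 50.3 | 23% | 62 | 97.3% | 26.0 |

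Two covariates cost two error degrees of freedom (118 to 116), which leaves these power figures unchanged to the decimal shown.

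**3. The same under the two-stage design.** The plan states no final critical value. With looks at 66 and 120 (information fraction 66/120 = 0.55), a first boundary of 2.28 and no futility stop, an overall two-sided 0.05 requires a final critical value of 2.088. Two-stage power is then 83.9% unadjusted, and 87.5 / 91.0 / 94.2 / 96.9% at R² = 0.1 / 0.2 / 0.3 / 0.4. The gains are of the same order as in the single-look table.

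**4. Chance imbalance.** The 95% range of the shift in the unadjusted estimate due to covariate imbalance alone is ±1.96 × 65 × √R² × √(4/N).

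- N = 120: √(4/120) = 0.183, giving ±7.4 at R² = 0.1 and ±12.7 at R² = 0.3 (mL/kg/d).
- N = 66: √(4/66) = 0.246, giving ±9.9 and ±17.2.

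These compare with a target difference of 36. The unadjusted standard error already allows for this shift, so it is not bias, but it is a component that adjustment would remove.

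**5. Does robust adjustment keep the protection Welch gives?** Under the null with 66 infants and |Z| > 2.28 (nominal 2.3%), simulation with two covariates gives rejection rates of 2.6% for the Welch Z, 2.4% for regression with HC1 standard errors and 2.0% with HC3. With three covariates and normal data the rates are HC0 3.3%, HC1 2.7% and HC3 2.2%. The protection is kept provided a small-sample version is named.

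**The case against.** The strongest case against is that nothing here is an error. Under randomisation the Welch test is unbiased, 104 is right for it, and 120 evaluable gives about 84% two-stage power, above the 80% target. Chance imbalance is already covered by the error rate and the confidence interval. **All of this stands**, and it is why the point concerns efficiency and not validity.

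The second argument is that R² may be low. Entry is restricted to 1,250 g or less and 32 weeks or less, intake is already per kilogram, all infants share the same limits on starting and advancing feeds, and advancement also depends on intolerance signs that arise after baseline. At R² = 0.05 fixed-sample power is 87.0%, and at 0.02 it is 86.0%, against 85.3% unadjusted. **This stands as a limit on the size of the gain.** It does not make adjustment harmful.

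Third, the SD refers to intake at 14 days, whereas Statistical Analysis speaks of total weekly intake, so the SD and R² may differ for the quantity actually tested. **This stands** as a further reason to read the table as illustrative.

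Fourth, the timing of SNAP II is not stated: Table 2 has the demographic row collected on entry and through the six weeks. **This stands for SNAP II only.** Gestational age and birth weight are fixed before randomisation, and the proposal does not depend on SNAP II.

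Finally, the term robust standard errors is too loose at 66 infants. **This is correct, and is met by naming HC3.**

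**Conclusion.** The concern holds. The primary test is unadjusted, no stratification factor is named, the plan itself identifies the drivers of feeding, and at least gestational age and birth weight are available for every infant before randomisation. Since those data are collected anyway, leaving them out of the analysis saves nothing.

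The direction of the loss follows from the plan's own account of feeding; its size does not. On an assumed R² of 0.1 to 0.4, with SD 65 and 60 per arm, fixed-sample power rises by about 3 to 12 percentage points (85.3% to between 88.7 and 97.3%), and the detectable difference falls by 1.7 to 7.5 mL/kg/d (33.5 to between 31.8 and 26.0). With a lower R² the gain is small. The change should be made because it is cheap and protects against a smaller effect than a 40-infant preliminary study suggested. The planned test is not invalid. The gain comes from adjustment; stratification alone would add little at this size.

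**What to change.** In Statistical Analysis, before any unblinded data are seen:

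- Make the primary analysis of P1.1 a linear regression on treatment, gestational age and birth weight. Report the treatment coefficient, which is still a difference in mean intake, with HC3 standard errors and a 95% confidence interval.
- Use the Z from this model at both the 66-infant and the 120-infant look.
- Decide in advance whether SNAP II is included. Include it only if it is defined as a value fixed before randomisation.
- Admit baseline values only. Kangaroo care, which Research Procedure calls potentially confounding, accrues after randomisation and does not belong in this model.
- Keep the Welch t-test as a supporting analysis, and use the same adjustment for the continuous secondary outcomes.

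The cost is wording in the analysis section, plus one sentence on SNAP II timing if it is used. No additional infants, visits or samples are needed, and the sample size can stay as it is.
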